1.2 Background to the Study Drug

Podofilox is an antimitotic drug which can be chemically synthesized or purified from the plant families *Coniferae* and *Berberidaceae* (e.g. species of *Juniperus* and *Podophyllum*).

RLD Condylox® Gel 0.5% is formulated for topical administration and supplied in 3.5 g aluminum tubes with an applicator tip. Each gram of drug substance contains 5 mg of Podofilox in a buffered alcoholic gel containing alcohol, glycerin, lactic acid, hydroxypropyl cellulose, sodium lactate, and butylated hydroxytoluene.

Podofilox Gel 0.5% must be applied to the warts surface with the applicator tip or finger. The Podofilox Gel 0.5% may cause skin irritation, and hence must not be applied to the unaffected skin areas. Treatment cycle consists of twice daily applications (morning and evening) for three consecutive days followed by a four day "rest" period. This one-week cycle may be repeated until there is no visible wart tissue or for a maximum of four cycles in total. Treatment should be limited to 10 cm² or less of wart tissue and to no more than 0.5 g of the gel per day.

1.2.1 Clinical Pharmacology

1.2.1.1 Mechanism of Action

Treatment of anogenital warts with Podofilox results in necrosis of visible wart tissue. The exact mechanism of action is unknown.

1.2.1.2 Pharmacokinetics

In systemic absorption study in 52 patients, topical application of 0.05 mL of an ethanolic solution containing 0.5% Podofilox to external genitalia did not result in detectable serum levels. ¹² Applications of 0.1 to 1.5 mL resulted in peak serum levels of 1 to 17 ng/mL one to two hours after application. The elimination half-life ranged from 1.0 to 4.5 hours. The drug was not found to accumulate after multiple treatments. ¹²

1.2.2 Clinical Experience

Following data is available for RLD Condylox® Gel 0.5% clinical trials.

In the first multicenter clinical study in 326 patients with anogenital warts, Condylox® Gel 0.5% and its vehicle were applied in a double-blind fashion to comparable patient groups. ¹³ Of the 260 patients with efficacy data, 176 were treated with Condylox® Gel 0.5%. Patients applied Condylox® Gel 0.5% twice daily for three consecutive days followed by a 4 day "rest" period. At the end of 4 weeks, 38.4% of the patients had complete clearing of the wart tissue when treated with Condylox® Gel 0.5%.

In the second multicenter clinical trial in 108 evaluable patients with anogenital warts, Condylox® (podofilox) Topical Solution 0.5% was compared with Condylox® Gel 0.5% for efficacy. As in the first clinical trial, patients applied Condylox® Gel 0.5% twice daily for three consecutive days followed by a four day "rest" period. Similar clearance rates were observed. At the end of 4 weeks, 25.6% of the patients had complete clearing of the wart tissue when treated with Condylox® Gel 0.5%. ¹⁴

Confidential Page 22 of 59

1.2.3 Safety Profile

In clinical trials with Condylox® Gel 0.5%, the following local adverse reactions were reported during the treatment of anogenital warts:

Table 2. Local adverse reactions reported in Condylox® Gel 0.5% clinical trials

Adverse Reaction	Mild	Moderate	Severe
Inflammation	32.2%	30.4%	9.3%
Burning	37.1%	25.9%	11.5%
Erosion	27.0%	20.8%	8.9%
Pain	23.7%	20.4%	11.5%
Itching	32.2%	16.0%	7.8%
Bleeding	19.2%	3.0%	0.7%

The severity of local adverse reactions was predominantly mild or moderate and did not increase during the treatment period. Severe reactions were most frequent within the first 2 weeks of treatment.

Other local adverse reactions reported included stinging (7%), and erythema (5%); less commonly reported local adverse events included desquamation, scabbing, discoloration, tenderness, dryness, crusting, fissures, soreness, ulceration, swelling/edema, tingling, rash, and blisters. The most common systemic adverse event reported during the clinical studies was headache (7%).¹⁴

Further details are provided in the Investigator's Brochure [IB]¹⁵.

1.3 Rationale of the Study

As stated in Section 1.2.1.2, topical application of 0.05 mL of an ethanolic solution containing 0.5% Podofilox to external genitalia did not result in detectable serum levels. In these settings, a conventional pharmacokinetic human study to demonstrate that Hyloris Developments SA Podofilox Gel 0.5% is bioequivalent to the Reference Listed Drug [RLD] Condylox® Gel 0.5% is not appropriate.

Hyloris Developments SA will initiate a clinical endpoint bioequivalence (BE) study for a Podofilox Gel 0.5% formulation for the treatment of external anogenital warts in comparison to Condylox® Gel 0.5% that follows the study design and recommendations according to Office of Generic Drugs (OGD) of U.S. Food and Drug Administration (FDA) Draft Guidance for Podofilox recommendations. ¹⁶

Confidential Page 23 of 59

2 STUDY OBJECTIVES AND ENDPOINTS

2.1 Study Objectives

2.1.1 Primary Objective

To compare the clinical efficacy among patients with anogenital warts when treated with Podofilox Topical Gel 0.5% versus Condylox® Gel 0.5% and placebo.

2.1.2 Secondary Objective

To demonstrate safety of Podofilox Topical Gel 0.5% compared to Condylox® Gel 0.5% and placebo assessed by the frequency and severity of adverse events, and application site reaction scores (erythema, dryness, burning/stinging, erosion, edema, pain, itching and bleeding).

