6.2.1.7 Assessment of Local Application Site Reactions

Local skin reaction scores for erythema, dryness, burning/stinging, erosion, edema, pain, itching and bleeding will be recorded by the Investigator for every study visit based on their intensity.

Table 4. Skin Reaction Scale

Reaction	Score, 0-3*
erythema	
dryness	
burning/stinging	
erosion	
edema	
pain	
itching	
bleeding	

^{*} Scores are: 0=absent, 1=mild (slight, barely perceptible), 2=moderate (distinct presence), 3=severe (marked, intense)

The Application Site Reaction Assessment must be conducted by qualified investigators listed on the Form FDA 1572 who have been delegated these tasks by the PI. The PI may delegate this task to Physicians, Physician Assistants, or Nurse Practitioners, Registered Nurses (RNs) or Licensed Practical Nurses (LPNs) who have documented training and past experience conducting this assessment.

Application site reactions (erythema, dryness, burning/stinging, erosion, edema, pain, itching, and bleeding) are to be recorded as adverse events of special interest.

All application site reactions must be recorded as adverse events in the source document and eCRFs.

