8 DATA ANALYSIS

The sections below summarize the intended statistical methods and analyses of data for the study. A more detailed statistical analysis plan will be written prior to finalization of the clinical trial database. Any changes to the planned methods and analyses will be described and justified in the protocol and/or in the final clinical study report, as appropriate.

Descriptive statistical methods will be used to summarize the data from this study, with confidence intervals calculated for the primary efficacy endpoints. Unless stated otherwise, the term "descriptive statistics" refers to number of subjects (n), mean, median, standard deviation (SD), minimum, and maximum for continuous data and frequencies and proportions for categorical data. The term "treatment group" refers to randomized treatment assignment: active-test and active-reference. All data collected during the study will be included in data listings. Unless otherwise noted, the data will be sorted first by treatment assignment, subject number, and then by date within each subject number.

Unless specified otherwise, all statistical testing will be two-sided and will be performed using a significance (alpha) level of 0.05.

All statistical analyses will be conducted with the SAS® System, version 9.4 or higher.

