8.3.4 Assessment of Safety

The reporting of safety data is descriptive, and will include all subjects who receive at least one dose of investigational product. The variables for safety endpoints are AEs, Local Application Site Reactions and vital signs measurements. AEs will be summarized based on the frequency of AEs and their severity for all treated subjects. All AEs will be coded using Medical Dictionary for Regulatory Activities (MedDRA) and summarized by treatment group. Data will be summarized using preferred term and primary system organ class.

Confidential Page 48 of 59

If a subject experiences multiple events that map to a single preferred term, the greatest severity and strongest Investigator assessment of relation to study drug will be assigned to the preferred term for the appropriate summaries. Should an event have a missing severity or relationship, it will be classified as having the highest severity and/or strongest relationship to study drug.

Summaries of treatment-emergent AEs will include any AEs reported beginning with the first dose of study drug on Day 1. The occurrence of treatment-emergent adverse events will be summarized by treatment group using preferred terms, system organ classifications, and severity. Separate summaries of treatment-emergent serious adverse events, treatment-emergent adverse events related to study drug, and events leading to the discontinuation of study drug will be generated. All adverse events reported will be listed for individual subjects showing both verbatim and preferred terms.

Concomitant medications will be coded using the World Health Organization (WHO) Drug Dictionary. These data will be summarized by treatment group. Previous and concomitant medications will be presented in a data listing.

Local Application Site Reactions will be recorded at each study visit and will be summarized by the type of reaction (erythema, dryness, burning/stinging, erosion, edema, pain, itching and bleeding) and intensity score: 0=absent, 1=mild (slight, barely perceptible), 2=moderate (distinct presence), 3=severe (marked, intense).

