3.1 Study Overview

Clinical study of protocol 016-POD-001 is a multicenter, parallel group, randomized, doubleblind, placebo-controlled, trial with clinical endpoint comparing Podofilox Topical Gel 0.5% to Condylox[®] Gel 0.5% and a matching placebo. The study will be conducted in adult male and female patients with external anogenital warts. The study also assesses comparative safety of Podofilox Topical Gel 0.5% and Condylox[®] Gel 0.5%.

Safety data analysis will include local application site reaction scores (erythema, dryness, burning/stinging, erosion, edema, pain, itching and bleeding), reported adverse events, vital signs and concomitant medication assessments summarized by treatment group and time point of collection, when appropriate.

The primary objective is to compare the clinical efficacy among patients with anogenital warts when treated with Podofilox Topical Gel 0.5% versus Condylox[®] Gel 0.5% and placebo. The secondary objective is to demonstrate safety of Podofilox Topical Gel 0.5% compared to Condylox[®] Gel 0.5% and placebo assessed by the frequency and severity of adverse events, and application site reaction scores (erythema, dryness, burning/stinging, erosion, edema, pain, itching, and bleeding).

The planned overall sample size for this clinical trial is approximately 413 adult male and female patients with external anogenital warts, who will be randomized at a 3:3:1 ratio (test: RLD: placebo) at about 16 clinical research centers in the United States, Russia and Ukraine. The mITT and PP population sizes will be approximately 392 and 350, correspondingly. A subject is considered enrolled after he/she has provided a signed informed consent and begins the screening process. A subject is considered randomized upon receiving his/her randomized treatment assignment.

Confidential

The entire study will consist of a maximum of 6 visits:

- 1. Visit 1 (Day -14 up to -1): Screening Evaluations at the Study Site performed.
- 2. Visit 2 (Day 0): Study Drug Dispensation.
- 3. Visit 3-5 (Day 7 ±1 [Week 1], Day 14 ±1 [Week 2], and Day 21 ±1 [Week 3]: Follow-up of the Study Drugs.
- 4. Visit 6 (Day 28 ± 5 [Week 4]): End of Study Visit / Early Termination Visit at the Study Site including Safety and Efficacy Evaluation.

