10 SAFETY ANALYSES

10.1 Safety Endpoints

The reporting of safety data is descriptive, and it will include all subjects who receive at least one dose of investigational product. The variables for safety endpoints are AEs, Local Application Site Reactions and vital signs measurements. Safety data will be summarized by treatment group and time point of collection, when appropriate.

Concomitant medications will be coded using the World Health Organization Drug Dictionary (WHO-DD). These data will be summarized by treatment group. Previous and concomitant medications will be presented in a data listing.

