10.1.1 Adverse Events

Adverse events will be coded using the most recent version of the Medical Dictionary for Regulatory Activities (MedDRA) and will be summarized based on frequency and severity of AEs for all treated subjects. Data will be summarized using preferred term and system organ classifications. Summary will show number and percentage of subjects who experience each AE.

If a subject experiences multiple events that map to a single preferred term, the greatest severity and strongest Investigator assessment of relation to study drug will be assigned to the preferred term for the appropriate summaries. Should an event have a missing severity or relationship, it will be classified as having the highest severity and/or strongest relationship to study drug.

Summaries of treatment-emergent AEs will include any AEs reported beginning with the first dose of study drug on Day 1. The occurrence of treatment-emergent adverse events will be summarized by treatment group using preferred terms, system organ classifications, and severity. Separate summaries of treatment-emergent serious adverse events, treatment-emergent adverse events related to study drug, and events leading to the discontinuation of study drug will be generated. All adverse events reported will be listed for individual subjects showing both verbatim and preferred terms.

Confidential

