10.1.2 Local Application Site Reactions

Local Application Site Reactions will be recorded at each study visit and will be summarized by the type of reaction (erythema, dryness, burning/stinging, erosion, edema, pain, itching and bleeding) and intensity score: 0=absent, 1=mild (slight, barely perceptible), 2=moderate (distinct presence), 3=severe (marked, intense The number and percentage of subjects affected will also be presented.

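### The safety objective is comparative, but the plan gives only side-by-side percentages by arm: no between-arm difference or interval, and 0–3 reaction scores shown only visit by visit

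*Protocol*

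**What the plan says.** Protocol 2.1.2 states the secondary objective as "To demonstrate safety of Podofilox Topical Gel 0.5% compared to Condylox® Gel 0.5% and placebo assessed by the frequency and severity of adverse events" and adds the scores for eight application site reactions. SAP 4.1 repeats it. A sentence in SAP 3.1 begins "The study also assesses comparative safety of Podofilox Topical Gel 0.5" and goes on to name the reference gel. Protocol 2.2.2 defines the reaction-score endpoint over the whole period of study drug application.

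The analysis is lighter than the objective. Protocol 8.3.4 says "The reporting of safety data is descriptive, and will include all subjects who receive at least one dose of investigational product", and SAP 10.1 says the same. The general text of Protocol section 8 describes descriptive methods "with confidence intervals calculated for the primary efficacy endpoints"; no interval is mentioned for safety.

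For the 0–3 scores, SAP 10.1.2 plans a summary by reaction and intensity and adds "The number and percentage of subjects affected will also be presented", without giving a time basis. The only shell for it, Table 14.3.7, is by visit.

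There is a second route. Protocol 6.2.1.7 says "All application site reactions must be recorded as adverse events in the source document and eCRFs". For repeated events under one preferred term, SAP 10.1.1 says "the greatest severity and strongest Investigator assessment of relation to study drug will be assigned to the preferred term". Table 14.3.8.1.2 shows the result by arm.

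**The concern.** An objective of demonstrating safety against two comparators asks how much more or less often a reaction occurs on the test gel, and how sure one can be of that. The planned output answers neither part directly. A statement that local tolerability matches the reference would rest on scanning many pairs of percentages, spread over eight reactions, several visits and the grades, with no stated precision.

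The endpoint that the protocol names, the 0–3 score over the application period, also has no period-level summary. What a reader wants is the share of subjects who ever reached moderate or severe. A by-visit table does not give that share.

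**Working it through.** **The plan's own figure.** There is no safety margin, alpha, power or precision in either document, so there is no safety figure to reproduce. The nearest stated figure is the bioequivalence probability of 0.92 in SAP 5.3. It reproduces (0.928 by exact enumeration, 0.924 by normal approximation) but says nothing about safety.

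**Step 1: objective against output.** The safety shells, Tables 14.3.7, 14.3.8 and 14.3.8.x, have columns for test, reference, placebo and all subjects. None has a column for a difference or an interval.

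**Step 2: can a per-subject worst score be read from Table 14.3.7?** Suppose, for illustration, that 5% of an arm scores 3 for one reaction at each of Visits 3 to 6.
- Same subjects each time: the share ever scoring 3 is 5%.
- Independent visits: 1 − 0.95⁴ = 18.5%.
- Different subjects each time: 4 × 5% = 20%.

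All three give the same table, so the per-subject rate is not recoverable from it.

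**Step 3: later-visit percentages.** Subjects whose warts clear finish the study at that visit (Protocol 3.1). SAP 7.4 bases percentages on all subjects in the treatment group, and SAP 7.6.5 imputes nothing for the Safety population. If a fraction c of an arm has cleared and left before a visit, and a share r of those examined has the reaction, the table shows r(1 − c).

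Take the assumed success rates in SAP 5.3, 40% active and 15% placebo, as outer bounds for c. The factors are 0.60 and 0.85. With r = 20% in both arms, the table would show 12% against 17%. The real effect is smaller, because some subjects clear only at the last visit. Test against reference is affected only if the timing of clearance or withdrawal differs between them.

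**Step 4: what precision would look like.** Inputs:
- 177 per active arm and 59 on placebo (SAP 5.3), treated as the safety population.
- Reference-gel rates from Protocol Table 2, assumed in both active arms, with grades taken as mutually exclusive.

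For test minus reference, the 95% Wald half-width is 1.96 × √(2p(1 − p)/177).

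| Reaction | p | Half-width |
|---|---|---|
| Severe burning or severe pain | 11.5% | 6.6 points |
| Moderate or severe burning | 25.9 + 11.5 = 37.4% | 10.1 points |
| Moderate or severe erosion | 20.8 + 8.9 = 29.7% | 9.5 points |

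Severe bleeding is left out: 0.7% of 177 is about one event per arm, too few for a Wald interval.

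For test minus placebo on severe burning, the documents give no placebo rate. Assuming 2% gives 1.96 × √(0.115 × 0.885/177 + 0.02 × 0.98/59) = 5.9 points. Assuming the same 11.5% gives 9.4 points.

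**The case against.** The strongest reply is that descriptive safety reporting is an open and legitimate choice, made in both documents. No decision rule uses a safety interval, so the sample size, the equivalence test and the superiority tests do not depend on one. That stands, and it limits this point to a mismatch of wording and a gap in presentation.

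Three stronger readings are tempting and are not supported:

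- *The safety analyses look at one arm at a time.* They do not. The shells set the three arms side by side, and Table 14.3.7 also has a row for reaction present and a change-from-baseline block.
- *No worst severity per subject is planned.* One is. Every site reaction is also an adverse event and enters Table 14.3.8.1.2 at its greatest severity. But Protocol 7.2 grades adverse events by tolerability and interference with usual activities, while Protocol 6.2.1.7 grades skin reactions by intensity. Marked erythema that disturbs nothing could score 3 on one scale and be mild on the other, and the objective lists the two measures separately.
- *The comparison cannot be made at all.* A reader can derive differences and intervals for adverse events from the printed counts, and visit by visit for the scores. The worst 0–3 score could be built from Listing 16.3.7. What is missing is a pre-specified summary.

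It is also fair to say that the half-widths reflect the sample size and would be the same with or without the change.

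**Conclusion.** The point holds as an inexpensive improvement. The documents set a comparative safety objective and a score endpoint over the application period, but plan no between-arm estimate or interval and no per-subject summary on the 0–3 scale. The by-visit table cannot supply that summary. Its later percentages can be diluted if the denominator rule in SAP 7.4 is applied literally.

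The half-widths of 6.6 and 10.1 points illustrate what the report would leave unsaid: with identical observed rates of 11.5% severe burning, an excess of up to about 6.6 points would still be compatible with the data. They rest on full planned enrolment, Table 2 rates in both active arms and a Wald interval, and should not be read as the size of an error in the plan. Nor should a reader infer any weakness in the bioequivalence or superiority conclusions from this point.

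**What to change.** In SAP 10.1.2, and in Protocol 8.3.4 if it is amended:

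- Derive each subject's worst post-baseline 0–3 score for each of the eight reactions.
- Report test minus reference and test minus placebo risk differences, with 95% score intervals (for example Miettinen–Nurminen), for score 2 or higher and for score 3. Score intervals also cope better with rare reactions.
- Do the same for subjects with any treatment-emergent event, a severe one, and one leading to discontinuation.
- Label all of it descriptive, with no p-values.
- Reword the objective so that it compares safety descriptively. Rewording alone would remove the mismatch in wording but would leave the score endpoint without a per-subject summary.

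The cost is one or two extra tables from data already collected. There would be up to 8 × 2 × 2 = 32 intervals for reactions and 3 × 2 = 6 for adverse events, 38 in all and unadjusted. Of the 19 test-minus-reference intervals, about 19 × 0.05 = 0.95 would be expected to exclude zero by chance if the two gels were alike, so the label matters. Editing the objective or Protocol 8.3.4 needs a protocol amendment under Protocol 9.7; the SAP change alone does not touch the protocol.

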2.2 Study Endpoints

2.2.1 Primary Endpoint

The primary endpoint is the proportion of subjects in the per protocol (PP) population with "treatment success" defined as "total disappearance of all warts within all treated areas".

2.2.2 Secondary Endpoint (Safety Endpoints)

Local application site reactions scores (erythema, dryness, burning/stinging, erosion, edema, pain, itching and bleeding) in each group during the study drug application period.

Other adverse events including serious adverse events throughout the study participation.

Confidential Page 24 of 59

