EAWs will be inspected and the count will be captured in the source worksheet and electronic Case Report Form (eCRF). The Investigator will assess the baseline level of Local Application Site Reactions, recording the scores on the Local Application Site Reactions Scale.

During the inspection, study physician (Principal Investigator (PI), or Sub-Investigator) will train the subject on proper application of the study drug using the demonstration tube (contains vehicle of the study drug) and applicator. The subject will be trained to apply the study drug to the surface of the warts at a proper amount (not to exceed 0.5 g per day or 0.25 g per application), avoiding unaffected and wounded skin areas, and to let the gel dry completely before allowing the return of opposing skin surfaces to their

Confidential Page 25 of 59

normal positions. Mirrors are to be used to facilitate the process of application. Subjects will be instructed to not use the study drug in the vagina or in the rectum, and remove medication from any areas that experience stinging or burning immediately upon application. A visual representation of this quantity will be showed to the subjects.

The subject will also be trained on Subject Diary Card completion and contraception methods. The subject will be given a kit of study drug, mirror and a Subject Diary Card to capture application details, and acknowledge any changes in skin reactions, other AEs and concomitant medications during the intervening time between the site visits.

On the following day after the Baseline visit (Day 1) the subject will apply the study drug on EAWs following the recommendations given at the training. The treatment phase will consist of four weekly treatment cycles at a maximum, during which the drug will be applied twice a day (in the morning and at the bedtime) for 3 consecutive days, then discontinuing for 4 consecutive days. Study drug will thus be applied only on Days 1, 2, 3, 8, 9, 10, 15, 16, 17, 22, 23 and 24.

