Study visits will occur on the seventh (7) day of each treatment cycle: on Day 7 (Week 1), Day 14 (Week 2), Day 21 (Week 3), and Day 28 (Week 4). Primary endpoint (total disappearance of all warts within all treated areas) will be evaluated during each of these visits. In case the primary endpoint is reached at any of the visits following Baseline, it will be considered as End of Study (EOS) visit – the Investigator will perform physical examination and repeat urine pregnancy test, and subject's participation will be considered completed. If reduction of warts is absent or incomplete, a new treatment cycle will be initiated for a maximum of four cycles in total for the subject.

During each study visit, the Investigator will collect vital signs, evaluate EAWs for healing, capturing the count, record Local Application Site Reactions and adverse events (AEs), assess Subject Diary Card completion and subject's compliance with the study drug application, review concomitant medication and confirm that there were no prohibited therapies applied from the last visit.

In the event the primary endpoint (total disappearance of all warts within all treated areas) has been achieved, this visit will be considered End of Study (EOS) visit. In case a subject discontinues prematurely, the Investigator will conduct an Early Termination (ET) visit, capturing the reason for discontinuation and performing assessments of EOS visit.

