6.2.3 Subject Diary Card Review

The subject will be given a kit of study drug, mirror and a Subject Diary Card to capture application details, and acknowledge any changes in skin reactions, other AEs and concomitant medications during the intervening time between the site visits. Subjects will fill out their diary cards during each treatment cycle noting the following:

- Time and date of application
- Any changes in skin reactions, other AEs and concomitant medication

Subjects will return their completed diary cards to the clinical site at each of the post-baseline visits (visits 3-5 and EOS/ET) for review and filing with the subject's source documents. The Investigator will verify that the subject complied with the application requirements. The study staff will sign off on completed diary card. Any missed application notations will be clarified with the subject and documented. Refer to Section 5.8 for additional information regarding the treatment compliance.

Confidential Page 37 of 59

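### Scheduled local reaction scores fall at the end of each rest period, and no worst-since-last-visit score is asked for, so the score endpoint can miss reactions on the application days

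*Protocol*

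**What the plan says.** The secondary objective (protocol 2.1.2) is to show the safety of the test gel against the reference and placebo, "assessed by the frequency and severity of adverse events, and application site reaction scores". It therefore has two components. Protocol 2.2.2 words the score component as "Local application site reactions scores (erythema, dryness, burning/stinging, erosion, edema, pain, itching and bleeding) in each group during the study drug application period" and does not define that period.

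Protocol 3.1 fixes the dosing days: "Study drug will thus be applied only on Days 1, 2, 3, 8, 9, 10, 15, 16, 17, 22, 23 and 24". The same section fixes the visits: "Study visits will occur on the seventh (7) day of each treatment cycle", namely Days 7, 14, 21 and 28. Under 6.2.1.7, scores for eight reactions on a 0-3 intensity scale "will be recorded by the Investigator for every study visit based on their intensity". No look-back period is given.

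Between visits, the diary (6.2.3) notes "Any changes in skin reactions, other AEs and concomitant medication". Section 6.2.1.7 also requires every site reaction to be recorded as an adverse event and treats these as events of special interest. Adverse event severity is graded under 7.2.

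On analysis, SAP 10.1.2 says: "Local Application Site Reactions will be recorded at each study visit and will be summarized by the type of reaction" and by intensity score. The shell for Table 14.3.7 gives the distribution at each visit and the change from baseline.

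**The concern.** The endpoint wording points to the time when the gel is being applied, but the schedule places the scoring at the end of the rest days. Protocol 3.1 itself foresees stinging or burning straight after application. A visit-day score need not reflect such a reaction unless someone is asked to look back over the cycle, and no passage asks for that.

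At stake is how informative one of the two safety components is. If the test and reference gels differ mainly in short-lived reactions on dosing days, by-visit scores could look similar across arms even though subjects' experience differed.

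**Working it through.** **Inputs.** Application days: 1, 2, 3, 8, 9, 10, 15, 16, 17, 22, 23, 24 (protocol 3.1). Visit days and windows: Day 0; Days 7, 14 and 21, each ±1; Day 28 ±5 (protocol Appendix B, SAP 7.6.3). Scoring takes place at Baseline and at each of these visits.

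**The plan's own figure.** Protocol 8.1 puts the final evaluation four days (±5) after the last day of the last cycle. The check is 28 − 24 = 4, which agrees.

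**Nominal timing.** Gap = visit day − most recent application day.

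| Visit | Day | Last application | Gap (days) |
|---|---|---|---|
| 3 | 7 | 3 | 4 |
| 4 | 14 | 10 | 4 |
| 5 | 21 | 17 | 4 |
| 6 | 28 | 24 | 4 |

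None of the four visit days is among the 12 application days. The Baseline score on Day 0 precedes all dosing.

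**Across the windows.**
- Visits 3-5 can fall 3 to 5 days after the preceding cycle's last application day (for example 6 − 3 = 3 and 8 − 3 = 5). The late edge (Day 8, 15 or 22) is the first application day of the next cycle. The documents do not say whether scoring would come before that day's first application.
- Visit 6 spans Days 23 to 33, which is 23 − 24 = −1 to 33 − 24 = +9 days from the last scheduled application day. Days 23 and 24 are application days.
- The windows therefore allow some scores on application days. The SAP has no rule to separate them in the by-visit table.

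**Two readings of the application period.**
- If it means the application days themselves, 0 of 4 post-baseline scores fall inside it at nominal timing.
- If it means Days 1 to 24 as a whole, 3 of 4 do (Days 7, 14 and 21) and Day 28 does not. Those three still sample only the last rest day of their cycles.

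**Other routes by which a between-visit reaction could reach the analysis.**
- Diary: section 6.2.3 lists changes in skin reactions as a topic and mentions no 0-3 grade. The SAP's only diary output, Listing 16.3.5, covers card dispensation, card return and compliance.
- Adverse events: these are tabulated by arm, preferred term and severity (SAP 10.1.1, Table 14.3.8.1.2). Severity under 7.2 depends on tolerability and effect on usual activities, which differs from the 0-3 intensity scale in 6.2.1.7. The list of tables has no special-interest table and none that relates onset to application days.
- Unscheduled visits (6.3.5) may include a reaction score, but only if required.

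These routes capture reactions, but they do not supply a 0-3 score for the dosing days.

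**The case against.** The strongest reply is that the objective does not rest on the scores alone. All site reactions must be recorded as adverse events and will be compared by arm and severity. Staff question subjects directly (6.2.1.8), the diary is reviewed at each post-baseline visit, and subjects are told to report reactions (5.7.1). Every arm uses the same adverse event scale, so a comparison between arms remains possible. Safety reporting is descriptive (protocol 8.3.4, SAP 10.1), and no equivalence decision depends on the scores. All of this stands. It confines the point to the score component.

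It also stands that the period in 2.2.2 is undefined and can be read as the whole treatment phase, and that 6.2.1.7 does not expressly limit the score to the subject's state at the visit. An investigator might take account of what the subject reports. With no look-back period stated, however, practice can differ between investigators and sites.

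A reader might go further and infer that reactions are subsiding by the visit, that all arms are pushed towards zero, or that a real difference would shrink by a calculable fraction. The documents do not support this. Protocol 1.2.3 says only that severe reactions were most frequent in the first two weeks; it gives no course within a cycle. Table 2 there reports reference-gel rates (burning of any grade is 37.1 + 25.9 + 11.5 = 74.5%) but not when they were assessed, so they cannot be taken as application-day rates. Nor do the documents give a rate at which reactions persist to the fourth rest day.

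**Conclusion.** The point holds for the score component of the secondary objective. At nominal timing all four post-baseline scores come 4 days after the last application, none of the 12 application days is scored, and neither document asks for a worst score or plans a summary of one. Reactions that arise and clear between visits can be missed by the scores and are left to the diary and adverse event records, where no 0-3 score is specified.

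This rests on nominal visit days and on reading 6.2.1.7 as setting no look-back period. How much is lost cannot be estimated from the documents.

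A reader might conclude that the endpoint as worded is not measured at all, or that the whole tolerability comparison fails. Neither follows. The first depends on one reading of an undefined period and ignores the windows; the second ignores the adverse event component. The primary endpoint, alpha and power are unaffected. This is an inexpensive improvement and does not call the trial's main conclusions into question.

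**What to change.** **If the forms can still change.**
- In protocol 6.2.1.7, have the investigator record two scores for each reaction at every post-baseline visit on the existing 0-3 scale: the current score, and the worst since the last visit, using the diary as an aid.
- In SAP 10.1.2 and Table 14.3.7, add the worst score by arm and label the existing by-visit scores as end of rest period, with a note that the windows allow some application-day scores.
- In protocol 2.2.2, define the application period.

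**If the forms can no longer change.** This may already be so, since SAP section 6 cites a note to file of 27 Feb 2019.
- Tabulate the site-reaction adverse events already collected by arm, maximum severity and onset relative to application days. Event start dates and times (Listing 16.3.8.1) and application times (Listing 16.3.4) are available. Leave imputed start dates out of the onset tabulation, because SAP 7.6.7 sets a completely missing start date to the date of first dose.
- Reword 2.2.2 to match when the scores are taken.

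**Cost.** The first option needs one more column on an existing form and one added summary, and accepts some recall error in the worst score. The fallback needs one table and a wording change. Neither adds visits or staff.
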